5.4.3 Prohibited Medications

The administration of any other anticancer agents including chemotherapy and biologic agents is NOT permitted, with the exception of hydroxyurea. Similarly, the use of other concurrent investigational drugs is not allowed unless specific approval has been obtained from the principal investigator AND the sponsors of BOTH investigational products. Red cell and platelet stimulating agents are not allowed on protocol. In life threatening situations, these can be given after permission from study PI.

5.5 Duration of Therapy

Duration of therapy will depend on individual response, evidence of disease progression and tolerance. In the absence of treatment delays due to adverse events, treatment may continue until one of the following criteria applies:

- Disease progression to acute leukemia unless, in the opinion of the principal investigator, the subject is experiencing clinical benefit from SGI-110 despite laboratory evidence of progression to acute leukemia.
- Intercurrent illness that prevents further administration of treatment,
- Unacceptable adverse event(s)
- Participant demonstrates an inability or unwillingness to comply with the medication regimen and/or documentation requirements
- Participant decides to withdraw from the study
- General or specific changes in the participant's condition render the participant unacceptable for further treatment in the opinion of the treating investigator.

5.6 Duration of Follow Up

Participants will be followed monthly for six months after removal from study or until death, whichever occurs first. Participants removed from study for unacceptable adverse events will be followed until resolution or stabilization of the adverse event.

Post-study case report forms will capture information including subsequent treatments, response to subsequent therapy, and survival.

5.7 Criteria for Removal from Study Treatment

Participants will be removed from study treatment for:

- Unacceptable adverse events that the in the opinion of the investigator is harmful to the participant
- Violation of the study plan or for administrative and/or other safety reason after discussion with the sponsor

CONFIDENTIAL

This document is confidential. Do not disclose or use except as authorized.

- Progression to Acute Myeloid Leukemia unless patient is deriving clinical benefit and it is in the opinion of the treating physician that the subject continue on the drug after discussion with the study PI.
- Progression of underlying disease (without transformation to AML) as specified in table 3.

The reason for study removal and the date the participant was removed must be documented. Alternative care options will be discussed with the participant.

When a subject discontinues/withdraws prior to study completion, all applicable activities for the final study visit should be performed at the time of discontinuation (after 28 days from last day or drug administration or before starting alternative treatment, whichever happens first). Any adverse experiences which are present at the time of discontinuation/withdrawal should be followed.

If a patient withdraws for non-medical reasons the following procedures will be followed:

- Physical examination will be performed.
- Safety assessment (physical examination, vital signs, hematology and serum chemistry), performed 30 days after last treatment

6. EXPECTED TOXICITIES AND DOSING DELAYS/DOSE MODIFICATIONS

Dose delays and modifications will be made using the following recommendations. Toxicity assessments will be done using the CTEP Active Version 4.0 of the NCI Common Terminology Criteria for Adverse Events (CTCAE).

If possible, symptoms should be managed symptomatically. In the case of toxicity, appropriate medical treatment should be used (including anti-emetics, anti-diarrheal, etc.).

All adverse events experienced by participants will be collected from the time of the first dose of study treatment, through the study and until the final study visit. Participants continuing to experience toxicity at the off study visit may be contacted for additional assessments until the toxicity has resolved or is deemed irreversible.

6.1 Anticipated Toxicities

6.1.1 Adverse Event List(s) for SGI-110

The most common AEs suspected by the investigators in Study SGI-110-01 to be related to the drug and observed to date in the MDS/AML population are: injection site pain, fatigue, nausea, thrombocytopenia, anemia and diarrhea. Based on the mechanism of action of the drug and its active form decitabine, myelosuppression (neutropenia, thrombocytopenia, and anemia) and the related consequences such as

CONFIDENTIAL

This document is confidential. Do not disclose or use except as authorized.

infection (e.g. pneumonia), sepsis, and bleeding are the most likely risks for the drug. Mucositis has also been reported.

Pain and burning at the injection site has been reported that are related to dose and volume of injection as well as the speed of injection. Care must be taken to avoid intradermal injection. Ice packs will be applied prior to injection of SGI-110 and the drug will be injected slowly, over 30-60 seconds. If the injection site events are reported at subsequent injections despite slow injection and the use of ice packs, pre-treatment with topical or systemic analgesics can be considered.

6.2 Dose Modifications for adverse events

All adverse events should be reported and considered as part of the overall safety evaluation of SGI-110. The Investigator should try to the best of his/her ability to assess whether an adverse event is related or unrelated to SGI-110. Dose modifications are not required for hematologic toxicities, but may be considered at the investigator's discretion, in collaboration with the Sponsor. In general, SGI-110 should be held for any:

1. Grade ≥ 3 non-hematologic toxicity (except nausea/vomiting, diarrhea) that fails to resolve to < grade 2 within 72 hours despite appropriate management.
2. Persistent grade ≥ 3 neutropenia or thrombocytopenia beyond day 56 of cycle 1 in the setting of a hypocellular bone marrow biopsy and absence of residual disease
3. Other clinically significant adverse event which, in the opinion of the Safety Review Committee (SRC), would place subjects at undue safety risk.

After resolution of toxicity, treatment with SGI-110 may be resumed at dose level of 45 mg/m². Retreatment at the original dose level may be considered, depending on the nature of the AE, and after discussion with the principal investigator. If the same toxicity that led to the dose reduction occurs again at this dose level, SGI 110 can be resumed at 30mg/m² after the toxicity has resolved to Grade ≤ 2 or baseline levels. Missed doses will be replaced at the investigator's discretion. Dose modifications for drug-related hematological toxicities will be managed on a case-by-case basis, depending on the patient's disease status and response to growth factor support, in collaboration with the principal investigator. There is no mandatory dose reduction or delay for hematological toxicity, but delays up to 14 days and dose reductions down to 30 mg/m² will be permitted depending on clinical circumstances, after discussion with the principal investigator. Additional delays or dose reductions may be considered after discussion with the principal investigator at Weill Cornell Medical Center.

7. DRUG FORMULATION AND ADMINISTRATION

7.1 SGI-110

CONFIDENTIAL

This document is confidential. Do not disclose or use except as authorized.

7.1.1 **Description**

Sodium (2*R*,3*S*,5*R*)-5-(4-amino-2-oxo-1,3,5-triazin-1(2*H*)-yl)-2-(hydroxymethyl)tetrahydrofuran-3-yl ((2*R*,3*S*,5*R*)-5-(2-amino-6-oxo-1*H*-purin-9(6*H*)-yl)-3-hydroxytetrahydrofuran-2-yl)methyl phosphate

7.1.2 **Form**

SGI-110 product is supplied in a two-vial configuration.

SGI-110 for Injection, 100 mg is a 5 mL glass vial containing lyophilized SGI-110 drug powder for reconstitution and subcutaneous injection using the custom diluent supplied in a separate vial. Each vial is stoppered with fluopolymer coated butyl rubber closure and sealed with a blue flip-off cap. *SGI-110 for Injection, 100 mg* vial is individually packaged in a heat-sealed aluminum foil pouch with a single desiccant bag to protect from moisture.

SGI-110 Diluent for Reconstitution, 3 mL is a 5 mL glass vial with 3 mL of custom diluent. Each vial is stoppered with fluopolymer coated butyl rubber closure and sealed with a white flip-off cap.

7.1.3 **Storage and Stability**

SGI-110 for Injection, 100 mg vial is stored at refrigerated condition of 2–8°C in the original packaging until use. *SGI-110 Diluent for Reconstitution, 3 mL* can be stored at 2–30°C in upright position until use. Both vials are preservative free and for single use only. SGI-110 must be stored in a secure, locked facility accessible only to authorized study personnel.

OSHA Guidelines for handling cytotoxic drugs outlined in the American Journal of Hospital Pharmacy must be followed.²² As with other potentially toxic anti-cancer agents, care should be exercised in the handling and preparation of SGI-110. The use of gloves and protective garments is recommended. Preparation should occur in a vertical laminar flow biological hood using proper aseptic technique. If SGI-110 contacts the skin, it should be immediately be treated with borax buffer solution pH 10 followed by washing immediately and thoroughly with soap and water. If SGI-110 contacts the mucous membranes, flush thoroughly with water.

Drug spilling can be inactivated by 2 N sodium hydroxide solution.

7.1.4 **Handling**

Qualified personnel, familiar with procedures that minimize undue exposure to themselves and the environment, should undertake the preparation, handling, and safe disposal of the chemotherapeutic agent in a self-contained and protective environment.

CONFIDENTIAL

7.1.5 Availability

SGI-110 is an investigational agent and will be supplied free-of-charge from Astex Pharmaceuticals.

7.1.6 Ordering and accountability

An initial supply of SGI-110 will be shipped to the investigational pharmacy when all the initiation documents, including IRB approvals and IRB approved ICF, have been received and reviewed by Astex Pharmaceuticals. Thereafter, it is the responsibility of the trial pharmacist to order a resupply.

SGI-110 must be kept in a locked limited access room. The study drug must not be used outside the context of the protocol. Under no circumstances should the Investigator or other study center personnel supply SGI-110 to other Investigators, subjects, or clinics or allow supplies to be used other than as directed by this protocol.

An accurate accounting of the study drugs and investigational devices must be maintained. These records must show dates, lot numbers, quantities received, dispensed, and returned and must be available for monitoring. SGI-110 accountability records must be maintained and readily available for inspection by regulatory authorities at any time.

7.1.7 Destruction and Return

At the end of the study, unused supplies of SGI-110 should be destroyed according to institutional policies. Destruction will be documented in the Drug Accountability Record Form.

8. CORRELATIVE/SPECIAL STUDIES

Bone marrow aspirate and peripheral blood will be collected for correlative scientific studies at the time of routine study assessments as detailed in the study calendar. Experimental work will be performed in the laboratories of [name]. and [name], Ph.D. The samples would consist of peripheral blood and bone marrow aspirate. Approximately 10mL of bone marrow aspirate (in a syringe with heparin) and up to 20mL of peripheral blood in purple or green top tubes will be collected at time points as indicated in the study calendar. The study samples will be stored indefinitely unless the study participant requests in writing that the study samples be destroyed.

9. STUDY CALENDAR

CONFIDENTIAL

This document is confidential. Do not disclose or use except as authorized.

Baseline evaluations are to be conducted within 2-week prior to start of protocol therapy with the exception of informed consent and bone marrow biopsy which may be performed within 28 days of first dose of study drug. In the event that the participant's condition is deteriorating, laboratory evaluations should be repeated within 48 hours prior to initiation of the next cycle of therapy

All assessments must be performed prior to administration of any study medication. All study assessments and medications should be administered within ± 5 days of the protocol-specified date, unless otherwise noted.

Assessment	Screening	Course 1 Day 1 (± 5 days)	Course 1 Day 14 (± 5 days)	Course ≥ 2 Day 1 (± 5 days)	Course ≥ 2 Day 14 (± 5 days)	Final Safety Evaluation Visit (28 days ± 2 after last study drug)
Physical examination ¹	X	X	X	X	X	X
Vital signs ²	X	X	X	X	X	X
CBC including manual differential	X	X		X	X	X
Blood chemistry ⁸	X	X	X	X	X	X
Urinalysis	X					X
ECG ³	X					X
LVEF ⁴	X					
Concomitant medication/non-drug therapies	X	X	X	X	X	X
Bone marrow aspiration or biopsy ⁵	X					X
Adverse events		X	X	X	X	X
Spleen measurement ⁶	X					X
QOL measurements ⁷		X		X		X
Research Studies (bone marrow aspirate, peripheral blood) ⁹	X		Xpb	Xpb		

1. Examinations will include assessment of extramedullary disease.

2. Vital signs will include weight, body surface area, body temperature (°C), pulse rate, and systolic and diastolic blood pressures.

3. Single ECGs will be obtained prior to first cycle only, repeat measurements based on clinical indication

4. Echocardiography or MUGA to be performed at baseline and repeated based on clinical indication. The same method that was used for Baseline LVEF determination will be used on repeat measurements.

5. Bone marrow samples will only be taken at baseline and the end of each cycle 3, 6 and 12. A confirmatory bone marrow will be needed 1 month after a CR/CRp is first detected by peripheral blood assessment confusing. Cytogenetics and molecular markers will be assessed only if a CR/CRp is obtained. Molecular marker assessment may be omitted if no molecular markers were detected at screening. Cytogenetics, immunophenotype and molecular markers may be obtained from the peripheral blood in the event of a dry tap.

6. Spleen size will be measured at baseline using US, MRI or CT at baseline and the end of cycle 3, 6 and 12. The same modality of imaging that was used at baseline will be used will be used for subsequent measurements (**IF NO SPLENOMEGLY PRESENT AT BASELINE EXAM AND NO SPLENOMEGLY ON PHYSICAL EXAM, US, MRI, CT MAY BE OMITTED AT SUBSEQUENT TIMEPOINTS**)

7. QOL measurements will be done using MFSAF scores at baseline and at beginning of every cycle.

8. Blood chemistry includes comprehensive metabolic panel, magnesium, phosphorus and uric acid, LDH

9. Research studies sample to be collected at baseline (Bone marrow) and day 14 of cycle 1 and then day 1 prior to each cycle from peripheral blood (pb). Research study samples from bone marrow (b) to be collected at the end of cycle 3, 6 and 12 as well as at the time of CR/CRp if the bone marrow biopsy is done outside the scheduled bone marrow biopsies per study guidelines.

CONFIDENTIAL

This document is confidential. Do not disclose or use except as authorized.

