2.5 Rationale

2.5.1 Both decitabine and SGI-110 have demonstrated safety and efficacy in patients with MDS, AML and CMML. Based on these data, substantial clinical experience and the lack of an effective treatment option in PHN-MPN, we hypothesize that treatment with SGI-110 will result in improved hematological and quality of life outcomes in patients with these diseases. SGI-110 will be administered subcutaneously at the dose level of 60mg/m² for 5 days to be repeated every 28 days. If the treating physician feels that SGI-110 needs to be started before 28 days for subsequent cycles, SGI-110 can be started before the 28 days in those clinical situations after getting permission from the study PI. To capture the potential ability of SGI-110 to improve both hematological and QOL measures, we will utilize a recently published composite endpoint for response assessment based on IWG-MDS, IWG-myelofibrosis and MFSAF (Myeloproliferative Neoplasm Symptom Assessment Form) tools: Savona et al., An international consortium proposal of uniform response criteria for myelodysplastic/myeloproliferative neoplasms (MDS/MPN) in adults. *Blood*, 125(12):1857-65.

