11. ADVERSE EVENT REPORTING REQUIREMENTS

11.1 Definitions

11.1.1 Adverse Event (AE)

An adverse event (AE) is any undesirable sign, symptom or medical condition or experience that develops or worsens in severity after starting the first dose of study treatment or any procedure specified in the protocol, even if the event is not considered to be related to the study.

Abnormal laboratory values or diagnostic test results constitute adverse events only if they induce clinical signs or symptoms or require treatment or further diagnostic tests.

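### No CBC is scheduled at Course 1 Day 14, so the first required post-dose blood count comes at about day 29

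*Combined protocol and SAP*

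**What the plan says.** Section 5.3.1 gives SGI-110 daily on days 1 to 5 of a 28-day cycle. In the Section 9 calendar the row "CBC including manual differential" is ticked at screening, Course 1 Day 1, Course ≥2 Day 1, Course ≥2 Day 14 and the final safety visit. The Course 1 Day 14 cell is empty. The physical examination, vital signs and chemistry rows are all ticked in that column, and footnote 9 places research sampling at "day 14 of cycle 1 and then day 1 prior to each cycle from peripheral blood (pb"). The same section states that "All study assessments and medications should be administered within ± 5 days of the protocol-specified date, unless otherwise noted", and it requires assessments to be completed before drug is given.

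Section 6.1.1 lists "myelosuppression (neutropenia, thrombocytopenia, and anemia) and the related consequences such as" infection, sepsis and bleeding as the most likely risks. Section 11.1.1 says that abnormal laboratory values "constitute adverse events only if they induce clinical signs or symptoms or require treatment or further diagnostic tests". Section 14.1 tabulates graded toxicities and puts exact 95% confidence intervals around the proportions.

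**The concern.** Course 1 is each patient's first exposure to a myelosuppressive drug, yet it has fewer scheduled blood counts than any later course, and no reason is given. Section 3.1 sets no neutrophil or platelet minimum for entry and admits patients with ECOG status up to 3, so some may start with little marrow reserve.

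Two things are at stake. The first is patient safety: a neutrophil or platelet nadir without symptoms can pass between scheduled counts, and nobody is required to look. The second, smaller matter is the safety summary: course-1 cytopenias that recover before Course 2 Day 1 may never be recorded.

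**Working it through.** **Inputs.** Course 1 Day 1 is day 1; the last course-1 dose is on day 5 (Section 5.3.1); cycles last 28 days; visits have a ±5-day window (Section 9). The plan states no figure of its own on this point, so there is none to reproduce.

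**First scheduled post-dose CBC as written.**
- Course 2 Day 1 = 1 + 28 = day 29; window 29 ± 5 = days 24 to 34.
- Time since last dose = 29 − 5 = 24 days; range 24 − 5 = 19 to 34 − 5 = 29 days.
- A patient who stops after course 1 has instead the final safety visit, 28 ± 2 days after the last drug: 5 + 28 = day 33 (31 to 35), or sooner if other treatment starts (Section 5.7).

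**With a CBC at Course 1 Day 14.**
- Window 14 ± 5 = days 9 to 19.
- Time since last dose = 14 − 5 = 9 days; range 9 − 5 = 4 to 19 − 5 = 14 days.
- Gain over Course 2 Day 1 = 29 − 14 = 15 days.

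**Nominal gaps between scheduled counts.**
- Course 1: 29 − 1 = 28 days.
- Later courses: 14 − 1 = 13 days, then 29 − 14 = 15 days (days counted within the course).

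**What each existing safeguard needs before it acts.**
- CBC with differential for febrile patients (Antibiotics paragraph, printed as 5.5.1): fever.
- Discretionary haematologic delay or dose reduction (6.2): a count that someone has seen.
- Section 6.2 items 1 and 3: a non-haematologic toxicity, or an adverse event judged clinically significant.
- 24-hour SAE reporting (11.4.1) and ad hoc DSMB review (12): a known event or safety issue.
- Adverse-event recording at the Day 14 visit: under 11.1.1, a laboratory value with consequences.

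None of these requires a count in a patient without symptoms between Course 1 Day 1 and Course 2 Day 1.

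**The case against.** The strongest reply is that Section 6.2 deliberately leaves haematologic toxicity to clinical judgement, that clinicians can draw unscheduled counts, and that febrile patients must have one. All of that is true, and it lowers the likely harm. It does not supply a required count in course 1, and it does not explain why later courses have one. It can also be said that 11.1.1 would keep many transient low counts out of the adverse-event tables even with a Day 14 CBC. That stands: any undercount is confined to counts that would have led to treatment or further tests.

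Two stronger readings are tempting, and the documents do not support them.

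*Early course starts are tied to no blood count.* A reader might infer this because 2.5.1 says "SGI-110 can be started before the 28 days in those clinical situations after getting permission from the study PI" without mentioning a count, and because the rule that "laboratory evaluations should be repeated within 48 hours prior to initiation of the next cycle of therapy" applies only to a deteriorating patient. But a CBC is ticked at Course ≥2 Day 1, and Section 9 puts assessments before dosing, so an early course still carries a count. The ±5-day medication window also yields where the protocol notes otherwise, as 2.5.1 does. What remains is narrow: the count may be several days old, and the PI's permission may come before it.

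*The day-56 hold does not fit the calendar.* Section 6.2 item 2 covers "Persistent grade ≥ 3 neutropenia or thrombocytopenia beyond day 56 of cycle 1 in the setting of a hypocellular bone marrow biopsy" without residual disease, and footnote 5 restricts marrow sampling to set times. But an on-time course 3 falls on day 1 + 2 × 28 = 57, where item 2 can act, and longer PI-agreed delays are allowed before then. Footnote 5 cannot be read literally either: the calendar ticks a marrow at the final visit, and footnote 9 provides for off-schedule marrows at CR/CRp. This is a matter of wording.

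**Conclusion.** The missing Course 1 Day 14 CBC is a real gap in scheduled safety monitoring and is worth correcting. In a continuing patient on schedule, it puts the first required post-dose count 15 days later than a Day 14 count would.

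The conclusion assumes that course 1 is dosed on days 1 to 5 and that course 2 starts on time; an early or delayed course 2 moves its CBC with it. It also assumes that the calendar cell is truly blank. The neighbouring rows are ticked in that column, which makes a lost tick unlikely, but the typeset table should be checked.

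A reader might go further and conclude that the reported toxicity rates will be materially biased. The documents give no rate of grade ≥3 cytopenia in this population and do not say how often unscheduled counts will be drawn, so no number of missed events can be claimed. Sample size, alpha, power and the 9-of-47 decision rule are unaffected.

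**What to change.** In the Section 9 calendar, add a CBC with differential at Course 1 Day 14, taken at the existing blood draw. The cost is one amendment and one extra CBC per patient, about 50 for the planned enrolment of 50.

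Three minor wording edits could go into the same amendment:
- In Section 9, state that dosing before 28 days follows the PI permission in 2.5.1 and not the −5-day side of the window, with the pre-dose Course Day 1 CBC seen by the PI. This costs a little scheduling flexibility.
- In calendar footnote 5, add *and when clinically needed to apply 6.2*.
- In 5.3.1, change the reference to 6.3.1, which does not exist, to 6.2.

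None of these adds a count threshold, a mandatory delay or a mandatory marrow, so the discretion in 6.2 stays as it is.
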